3. Affix **postage** and **address labels**.
4. Deliver to appropriate mailing deposit/box.

To simplify Mailing 2, study coordinators are encouraged to create separate files/sectionals for the two versions of the Visit 1 appointment packets (i.e. pre-visit prep and no pre-visit prep). The Pre-Visit Guide and Question Prompt List can be pre-printed together and enclosed in an individual envelope with a pre-visit envelope label. Those envelopes can be stored alongside the Instruction sheet A and Information sheet A. A separate file/sectional can house the contents of the Version B packet for the packets without Pre-Visit Preparation: Instruction Sheet-B and Information Sheet-B.

The Intake Survey is **child-age specific** and does not differ across pre-visit prep assignments. Be sure to include the correct version of the survey for the participant. Include the survey version for the age of the participant at the time that their eligibility was determined.

Important notes about age in NCGENES 2: Pediatric participants in NCGENES 2 must be <16 years at eligibility determination. Intake surveys sent to parent participants are based on the child's age at their determination of eligibility. The following table clarifies the age ranges found on intake surveys:

Survey Age Bracket	Clarified Age Range
1-12 mos	From birth until 1 day prior to 1st birthday (includes infants <1 month old)
13-24 mos	From 1st birthday until 1 day prior to 2nd birthday
2-4 yrs	From 2nd birthday until 1 day prior to 5th birthday
5-7 yrs	From 5th birthday until 1 day prior to 8th birthday
8-12 yrs	From 8th birthday until 1 day prior to 13th birthday
13-18 yrs	From 13th birthday until 1 day prior to 16th birthday (excludes patients >16 years old)

Relevant Documents

Document	File Name (Names in italics vary by site/clinic)
Visit 1 Appointment Reminder Letter	NCGENES_2_V1_Appt_Reminder_Letter_Mail_Merge_[DATE]
Intake Survey	Intake Survey [DATE] for [Age Range] clean
Information Sheet	NCGENES_2_Information_sheet_Version_A_clean_[DATE] NCGENES_2_Information_sheet_Version_B_clean_[DATE]
Instructions Sheet	NCGENES 2 Instructions Sheet with Previsit [DATE] NCGENES 2 Instructions Sheet without Previsit [DATE]
Pre-Visit Booklet	Pre-Visit Booklet_post CCT input -- FINAL [DATE]
Question Prompt List	NCGENES QPL_1 page flyer [DATE]-jsb cr.pptx
Mail Merge Excel Document	NCGENES2_Visit_1_Appointment_Packet_- _without_Pre_Visit_Prep_[DATESTAMP].xlsx NCGENES2_Visit_1_Appointment_Packet_- _with_Pre_Visit_Prep_[DATESTAMP].xlsx

Mailing 3 – Pre-RoR Packet

Adult participants who consent (with assent as necessary) to the Randomization to Genome Sequencing will receive some version of a Pre-Return of Results Packet regardless of their randomization to intervention 1 or 2. This mailing contains a letter reminding parents that they will receive a survey after they've received results. Participants randomized to exome sequencing and pre-visit prep will also receive some pre-return of results educational materials.

To Complete this Mailing:

1. **For participants randomized to receive Exome Sequencing and Pre-Visit Prep:**
 - a. Download the “pre-RoR Packet Letter – GS and Prep” letter from **IRBIS**, complete the **mail merge**, and print.
 - b. Print and attach the Pre RoR prep brochure with Question Prompt List
2. **For all other participants**, download the “pre-RoR Packet Letter – NO RoR” letter from **IRBIS**, complete the **mail merge**, and print.
3. Affix **postage** and **address labels**.
4. Deliver to appropriate mailing deposit/box.

Relevant Documents:

Document	File Name (Names in italics vary by site/clinic)
Pre-RoR Packet Letter	NCGENES_2_pre-RoR_PACKET_Letter_GS_and_Prep_Arm_[DATE] NCGENES_2_pre-RoR_PACKET_Letter_NO_RoR_Prep_[DATE]
Pre RoR Prep brochure	NCGENES 2 pre ROR prep_FINAL
Mail Merge Excel Document	NCGENES2_Pre-RoR_Packet_-_No_GS_without_Pre-Visit_Prep_[DATESTAMP].xlsx NCGENES2_Pre-RoR_Packet_-_GS_without_Pre-Visit_Prep_[DATESTAMP].xlsx NCGENES2_Pre-RoR_Packet_-_GS_with_Pre-Visit_Prep_[DATESTAMP].xlsx

Mailing 4 – 2 Week Post-RoR Parent Survey

Adult participants who consent their children (with assent as necessary) to the Randomization to Genome Sequencing will receive some version of a Post-RoR 2 week survey regardless of their randomization to intervention 1 or 2. This mailing contains a cover letter and one of four surveys depending upon the participant.

To Complete this Mailing:

1. Download the RoR 2 Week Survey Letter from [IRBIS](#), complete the [mail merge](#), and print.
 - a. **For participants consented to genome sequencing:**
 - i. *If the participant was randomized to Pre-Visit Prep*, attach the “RoR 2 Week Parent Survey [DATE] Paper ES and Previsit Prep” Survey
 - ii. *If the participant was randomized out of Pre-Visit Prep*, attach the “RoR 2 Week Parent Survey [DATE] Paper ES and NO Previsit Prep” Survey
 - b. **For participants who did not receive genome sequencing:**
 - i. *If the participant received some diagnostic testing*, attach the “RoR 2 Week Parent Survey [DATE] Paper No ES and Diagnostic Testing” Survey
 - ii. *If the participant did not receive any diagnostic testing*, attach the “RoR 2 Week Parent Survey [DATE] Paper No ES and No Diagnostic Testing” Survey
2. Create a return envelope and include in the mailing
3. Affix [postage](#) and [address labels](#).
4. Deliver to appropriate mailing deposit/box.

Relevant Documents:

Document	File Name (Names in italics vary by site/clinic)
RoR 2 Week Survey Letter	RoR 2 week survey cover letter_[DATE]
RoR 2 Week Surveys	RoR 2 Week Parent Survey [DATE] Paper ES and Previsit Prep RoR 2 Week Parent Survey [DATE] Paper ES and NO Previsit Prep RoR 2 Week Parent Survey [DATE] Paper No ES and Diagnostic Testing RoR 2 Week Parent Survey [DATE] Paper No ES and No Diagnostic Testing
Mail Merge Excel Document	NCGENES2_Post-RoR_- _Parent_2_Week_Questionnaire_Mailing_[DATESTAMP].xlsx

Mailing 5 – Gift Card and Thank You for 2 Week Survey

Whenever a completed 2 week Post-RoR Parent Questionnaire is returned by the parent, a thank you card should be sent to the parent along with a gift card for \$30 (See [Tracking Participant Compensation](#)). This mailing should be sent even if the survey was completed outside the technical window for completion.

To Complete this Mailing:

1. In a thank you card, write the following message:

“Thank you for completing and returning your survey! It will be a few months before the next study step which is a survey. Please let us know if you have any questions or changes to your contact information. Thank you for your continued participation in NCGENES!
[include a name and best contact method #]”
2. Place a gift card in the thank you card and place both in an envelope.
3. Affix [postage](#) and [address labels](#) (using [mail merge](#) from tracking system).
4. Deliver to appropriate mailing deposit/box.

Relevant Documents:

Document	File Name (Names in italics vary by site/clinic)
Mail Merge Excel Document	NCGENES2_Post-RoR_- _Parent_2_Week_Questionnaire_Gift_Card_Mailing_[DATESTAMP].xlsx
Thank You Text	Text_inside_Thank_You_Notes_NCGENES_[DATE]

Mailing 6 – 6 Month Post-RoR Parent Survey

Adult participants who consent their children (with assent as necessary) to the Randomization to Genome Sequencing will receive some version of a Post-RoR 6 month survey regardless of their randomization to intervention 1 or 2. This mailing contains a cover letter and one of several surveys depending upon the participant's age and clinical history.

To Complete this Mailing:

1. Download the RoR 6 month Survey Letter from [IRBIS](#), complete the [mail merge](#), and print.
 - a. **For participants consented to genome sequencing**, attach the "RoR 6 Month Parent Survey [DATE] [AGE RANGE] Paper Diagnostic Testing" Survey for the age of the participant.
 - b. **For participants who did not receive genome sequencing:**
 - i. *If the participant received some diagnostic testing*, attach the "RoR 6 Month Parent Survey [DATE] [AGE RANGE] Paper Diagnostic Testing" Survey for the age of the participant.
 - ii. *If the participant did not receive any diagnostic testing*, the "RoR 6 Month Parent Survey [DATE] [AGE RANGE] Paper NO Diagnostic Testing" Survey for the age of the participant.
2. Create a return envelope and include in the mailing
3. Affix [postage](#) and [address labels](#).
4. Deliver to appropriate mailing deposit/box.

The 6 month Post-RoR Survey is **child-age specific**. Be sure to include the correct version of the survey for the participant. Include the survey version for the age of the participant *at the time of the survey's mailing*.

Important notes about age in NCGENES 2: Pediatric participants in NCGENES 2 must be <16 years at eligibility determination. Intake surveys sent to parent participants are based on the child's age at their determination of eligibility. The following table clarifies the age ranges found on intake surveys:

Survey Age Bracket	Clarified Age Range
1-12 mos	From birth until 1 day prior to 1st birthday (includes infants <1 month old)
13-24 mos	From 1st birthday until 1 day prior to 2nd birthday
2-4 yrs	From 2nd birthday until 1 day prior to 5th birthday
5-7 yrs	From 5th birthday until 1 day prior to 8th birthday
8-12 yrs	From 8th birthday until 1 day prior to 13th birthday
13-18 yrs	From 13th birthday until 1 day prior to 16th birthday (excludes patients >16 years old)

Relevant Documents:

Document	File Name (Names in italics vary by site/clinic)
RoR 6 Month Survey Letter	RoR 6 month survey cover letter_[DATE]
RoR 6 Month Surveys	RoR 6 Month Parent Survey [DATE] [AGE RANGE] Paper NO Diagnostic Testing RoR 6 Month Parent Survey [DATE] [AGE RANGE] Paper Diagnostic Testing
Mail Merge Excel Document	NCGENES2_Post-RoR_- _Parent_6_Month_Questionnaire_Mailing_[DATESTAMP].xlsx

Mailing 7 – Final Gift Card and Thank You for 6 Month Survey

Whenever a completed 6 month Post-RoR Parent Questionnaire is returned by the parent, a thank you card should be sent to the parent along with a gift card for \$60 (See [Tracking Participant Compensation](#)). This mailing should be sent even if the survey was completed outside the technical window for completion.

To Complete this Mailing:

1. In a thank you card, write the following message:
“Thank you for completing your final survey with NCGENES 2!
[include a name and best contact method #]”
2. Place a gift card in the thank you card and place both in an envelope.
3. Affix **postage** and **address labels** (using **mail merge** from tracking system).
4. Deliver to appropriate mailing deposit/box.

Relevant Documents:

Document	File Name (Names in italics vary by site/clinic)
Mail Merge Excel Document	NCGENES2_Post-RoR - _Parent_6_Month_Questionnaire_Gift_Card_Mailing_[DATESTAMP].xlsx
Thank You Text	Text_inside_Thank_You_Notes_NCGENES_[DATE]

USING THE TRACKING SYSTEM

A web-based tracking system has been developed for the management of the NCGENES 2 project. The tracking system originates, facilitates and/or records every study activity. In other words, it is the central tool of study staff. The tracking system can be accessed in several different ways. Users should be cautious of which site they are using, as any data entered on the live site will be part of the study record.

Each study location (UNC, Mission, ECU) has a corresponding tracking site independent from the others. While the URLs for each are identical, a user's log-in information will dictate which tracking site they view. The study location of a tracking site will be indicated in its header (See [Homepage](#) on page 61). If a study staff member has different roles at multiple sites, they will need different log-in credentials in order to access each site separately.

Live Site: <https://ncgenes2.sirs.unc.edu/>

The live site is the main hub for study operation.

Demo Site I: <https://ncgenes2.sirsdemo.unc.edu/>

This demo version of the site was used for development of pre-visit and visit 1 tasks and can be used for training purposes. Data input here does not enter the study record. Additionally, alert protocols created by the Demo Site will not trigger emails to the clinical project director.

Demo Site II: <https://ncgenes2-ror.sirsdemo.unc.edu/>

This demo version of the site is used for development of return of results tasks and can also be used for training purposes. Data input here does not enter the study record. Additionally, alert protocols created by the Demo Site will not trigger emails to the clinical project director.

Survey Site: <https://ncgenes2.sirs.unc.edu/surveys>

The survey site is used to complete parent surveys. Each survey requires a unique code and parent's completing surveys using this site cannot access other data in the tracking system.

Provider Site: <https://ncgenes2.sirs.unc.edu/>

[figure not shown]
Provider's share a log-in page with other study staff but see a unique version of the site. Provider's only access surveys and result information for their patients.

This section covers the basic functions of the tracking system, key terminology, important tools within the tracking system and tracking system roles. Later on, the protocol provides more detailed instructions for completing specific tasks within the tracking system.

Logging In

[figure not shown]
The following covers logging in to the live tracking site with appropriate screenshots. The same procedures can be used to access either demo version of the site.

1. In a web browser, navigate to <https://ncgenes2.sirs.unc.edu/>. The following page will appear:

[figure not shown]
The screenshot shows the 'Login' page for NCGENES 2. The page has a header 'NCGENES 2' on the left and a 'Login' link on the right. The main area is titled 'Login' and contains fields for 'E-Mail Address' and 'Password', both with placeholder text. Below these is a 'Remember Me' checkbox and a 'Login' button. To the right of the 'Login' button is a 'Forgot Your Password?' link.

2. If this is your first time accessing the system, you'll need to create a password. Steps 3 through 7 will cover this process. If you already have a password, simply enter your email and password in the appropriate boxes and click the blue "Login" button to log in.
3. If you need to create a password, or if you cannot remember your password, click the "Forgot Your Password?" link just to the right of the "Login" button. The following page will appear:

[figure not shown]
The screenshot shows the 'Reset Password' page for NCGENES 2. The page has a header 'NCGENES 2' on the left and a 'Login' link on the right. The main area is titled 'Reset Password' and contains a field for 'E-Mail Address'. Below this is a 'Send Password Reset Link' button.

4. Enter your email address into the appropriate box, and click the "Send the Password Reset Link." One of two things will happen at this point.
 - a. If the following screen appears (next page), you may not have been added as a user to the tracking system. If you receive this message, contact the project coordinator ([contact]) or study director ([contact]) to resolve the issue.

The screenshot shows the 'Reset Password' page with an error message. The 'E-Mail Address' field is highlighted with a red border. Below the field, the text 'We can't find a user with that e-mail address.' is displayed in red. The 'Send Password Reset Link' button is visible at the bottom of the form.

b. In most cases, the following screen will appear:

NCGENES 2

Reset Password

[figure not shown]
We have e-mailed your password reset link!

E-Mail Address

Send Password Reset Link

Login

5. If you receive this message, proceed to your email inbox and look for an email from [contact]. The email should look like this:

NCGENES 2

Hello!

[figure not shown]
You are receiving this email because we received a password reset request for your account.

Reset Password

If you did not request a password reset, no further action is required.

Regards,
NCGENES 2

6. Click the blue “Rest Password” button, which will open a new browser window (or tab) displaying the following page:

NCGENES 2

Reset Password

E-Mail Address

Password

Confirm Password

Reset Password

Login

7. Enter your email, new password twice in the appropriate boxes. Then press the blue “Reset Password” button. You will be automatically logged in at that time. Remember to keep track of your password for future logins.

Key Terminology: Task v. Status

Two terms, task and status, are central to the functioning of the tracking system. Unfortunately, these terms are also easily conflated.

Tasks

Study activities are captured in the tracking system as tasks. A task is completed by study staff in accordance with wider protocol. For example, the study coordinator will complete the “Enrollment Call” task while they call a parent and attempt to enroll them. As a participant moves through the study, the completion of tasks will trigger subsequent tasks. At a given time, a participant may have several tasks pending. A participant’s tasks are listed on their [individual page](#) (see page 67).

Statuses

Unlike tasks, a participant can only have one status at a time. Statuses capture a participant’s progress through the study. For instance, a participant whose parent has completed the enrollment call and consented will have the status of “Parent Consented.” Participants with similar statuses are in the same phase of the study. Several statuses in the study are final statuses. As the name indicates, final statuses do not change and indicate a participant’s final state in relationship to NCGENES. [Appendix II](#) contains a full diagram of study statuses. A participant’s current status is listed on the [Participants List](#) (see page 62) or on the participant’s [individual page](#) (see page 67).

Status v. Assignment Statuses are distinct from selection and randomization assignments. NCGENES 2 has 1 selection and 2 randomizations. For each participant that reaches those points of the study, their selection or randomization assignment will appear to the right of their name on their [individual page](#) (see page 67). A participant can have more than one assignment at one time (in addition to their status) and keeps any assignment throughout the study.

Main Tracking System Pages

Every tracking system user will frequently encounter a few main pages. In order to orient a potential user, this section contains a screenshot of each page with detailed breakdown of their components. The pages covered are the homepage, participant list, mailings page, documents page, and individual participant interface.

Homepage

Upon logging in to the tracking system, users are directed to the homepage. The homepage lists incomplete study tasks by order of their due date. All study activities logged in the tracking system are captured as **tasks**. As tasks are completed, new tasks are assigned and given due dates by the system based on study protocol.

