2. able to sign legal documents for your child (excludes foster parents)
3. willing and able to attend the study-related clinic visit

¹ All statuses entered manually are *final statuses*. Only tracking system administrators can change these statuses once they are set.

4. able to complete surveys in English (NOTE: Spanish enrollment is planned for the future)

If the study coordinator reaches the parent and performs the parent eligibility screening, the enrollment status will automatically update to ‘PARENT ELIGIBLE’ or ‘PARENT INELIGIBLE’. ‘PARENT INELIGIBLE’ is a final study status and no further action is required. Those parents determined to be eligible will continue to the next step: parent consent to intervention/randomization 1.¹

Mark Participant as Refused Manually²

A participant’s status should be manually marked refused when a participant refuses to complete a study activity. This is initiated by the participant and occurs during a data collection activity (e.g., enrollment call, pre-visit survey, post-visit survey). Detailed instructions for changing a participant’s status manually can be found in the “[Using the Tracking System](#)” section of the protocol on page 70.

Parent Consent

Eligible parents will be invited to participate in the study and consented. If the study coordinator consents the parent, the enrollment status will be updated to ‘PARENT CONSENTED’. Parents who refuse or decline to consent will have an updated status of ‘REFUSED-AT ENROLLMENT (INTERVENTION I)’. The status change is triggered when a parent answers “no” to the question: Do you want to join the first part of the NCGENES research study? All parents who decline/refuse participation will be asked if they would like to indicate a reason for their decision. If a reason is provided, it should be recorded in the tracking system when the participant’s status is changed.

Randomization 1

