Parents who consent to be in the first part of the study will be randomized into either the pre-visit education or no pre-visit education groups (i.e. intervention 1). The group assignment will be based on a block randomization scheme. A participant is randomized into a group when the study coordinator clicks “Yes” and “Next” in the consent part of the enrollment call that is captured in the tracking system (See on page 90). The status determination will automatically appear on the next screen in the tracking system.³ Based on this status (and after conclusion of the call), the study coordinator or another unblinded study staff person should mail a Pre-Visit Packet to the participant with or without Prep materials (See [Mailing 2](#) in the participant mailings section on page 51).

Protocol if unable to complete enrollment call

For any attempts to contact the parent for the enrollment call, the following statuses should be recorded in the communication log⁴ as appropriate, along with any additional relevant information:

- Parent not available
- No one answers the telephone
- Call disconnected
- Wrong phone number
- Phone disconnected

Provider Notification of NCGENES 2 Participant

¹If the parent is determined to be eligible **but** the enrollment call is not completed, the participant’s status will be “PARENT ELIGIBLE” until the call is completed. This situation can occur, when the parent does not have time to complete the enrollment call, so the call is scheduled for a future date/time.

² All statuses entered manually are **final statuses**. Only tracking system administrators can change these statuses once they are set

³If the tracking system fails at this point in the call, the study coordinator should complete the call and inform the parent they will learn their group assignment when they receive the study materials. Then the coordinator should inform the Sheps team of the tracking system failure and ask that they provide the intervention 1 assignment. Once this information is obtained study Mailing 2 should occur and the tracking system updated once the failure has been resolved.

⁴For detailed instructions on using the communication log, see the “[Using the Tracking System](#)” section of this protocol on page 60.

After a participant has been enrolled, study staff must notify the clinician of their patient's status as an NCGENES 2 participant. The protocol for this notification varies by clinic.

UNC Genetics and Metabolism Clinic

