When parent has checked into the clinic and the child has been offered the iPad (if parents allow), the RA should confirm the Visit 1 details. The purpose of this task is to confirm the participant’s appointment date and provider. This is particularly important if a participant ends up being seen by a different physician in a particular clinic. Confirmation of this sets the NCGENES visit 1 date for the study. Detailed instructions on completing this task can be found in the “[Tracking System Tasks](#)” section on page 95. Following the appointment date and provider confirmation, the RA should turn their attention to the parent and remind the parent about what will happen during the visit and should ask the parent if they have brought their completed intake survey.

Collecting the Intake Survey

Participants should have completed the Intake Survey prior to their research visit and should have brought the completed document with them to the clinic. If the participant has their completed form, collect it at the beginning of the research appointment. When you collect the document briefly check for its completion (especially for the child’s partial social security number)-this step can also be done while the parent is completing the pre-visit survey. Record the collection of the completed Intake Survey in the participant tracking system by completing the “[Visit 1-Collect Info about Intake Completion](#)” task.

Parent forgot their completed intake survey? If the participant completed the survey at home but failed to bring it with them to the study visit, provide the parent with a labeled envelope with prepaid postage and a blank copy of the intake form (in case the parent cannot locate the completed form). Inform the parent that they should use the provided envelope to return the survey by mail.

Parent didn’t complete intake survey? If the participant did not complete the Intake Survey, two things can be done:

1. If the participants arrive with substantial time before their doctor visit, parent can complete intake form in the clinic after completing the pre-visit survey.
2. If the participant cannot complete the survey in clinic, parent should be provided with another Intake Survey with a labeled envelope with prepaid postage. Inform the parent that they should use the provided envelope to return the Intake Survey by mail.

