[Study Withdrawal & No Show Protocol](#)

The protocols in this section involve changing a participant's status using the "Change Status" button on the individual participant's page in the tracking system. Further instructions on this process, can be found in the "[Using the Tracking System](#)" section on page 70.

Withdrawal

A participant could be considered withdrawn under two circumstances:

1. When a participant asks to be withdrawn from the study. When this request occurs, a withdrawal form is completed by the study coordinator or RA. This request is initiated by the participant and occurs at any time.
2. Or, during study contact for non-data collection activities, such as making the reminder call. This action is initiated by a member of the study team.

In either case, the participant should be marked "Withdrawn."

Investigator Withdrawal

Participants are subject to investigator withdrawal when:

1. A pediatric patient is found to have a confirmed genetic related diagnosis during Visit 1. This would be considered “Investigator Withdrawal-At Clinic Visit 1 (Intervention 1)”. These participants will/can complete the Intake Survey, Pre- and Post-Visit Surveys but are not considered for Genetic Sequencing part of the study (i.e. intervention 2). Parents can receive up to \$70 in compensation, and the child will receive a nonmonetary gift.
2. NCGENES study staff unable to attend the research/clinic appointment (e.g. due to illness or other conflict). Participants that attend their clinical appointments, can receive up to \$40 (\$10 for parking and \$30 if they submit a completed Intake Survey).
3. A participant (child or adult) was ineligible at the time of enrollment BUT this was only discovered after participant was already enrolled (e.g at Visit 1). For example, a participant has a confirmed genetic diagnosis prior to the enrollment (i.e. this diagnosis does not occur at Visit 1), but this diagnosis was not disclosed during the enrollment call and was not found in the patient’s medical record. In these cases, all the data associated with this participant will be removed for the analytic database.

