3. If necessary, select the “Create Appointment” button to set an appointment in conjunction with the communication log.

Add Communications Log

Date & Time 05/04/2019 9:44pm

Subject Recruitment

Channel in person

Status Reached

Notes

Create Appointment

Type

Staff

Date & Time

Notes

Close Save changes

4. In either case, click the “Save changes” button at the bottom of the box. The communication will then be saved and visible from the Communication Log tab on the participant’s page.

Status Dates

The Status Dates tab displays all the statuses associated with the study. If a participant currently has or has previously had that status, the date of that status will be displayed. Otherwise, the status will display as “blank.”

Consented To Gs Rand

Visit 1 Appointment: [REDACTED]

ID# [REDACTED] MRN: [REDACTED] Site: UNC | Clinic: Pediatric Genetics and Metabolic | DOB: [REDACTED]

Log Communication Edit Info Schedule Remind **Change Status** ▾

Tasks Communication Log Schedule Status Dates History Notes Documents

Event	Date
participant_eligible_at	07/06/2019
participant_ineligible_at	blank
selected_at	07/06/2019
not_selected_at	blank
selection_complete_at	07/06/2019
parent_eligible_at	07/09/2019
parent_ineligible_at	blank
parent_consented_at	07/09/2019
parent_refused_at	blank
approached_at	07/09/2019
randomized_at	07/09/2019
consent_to_gs_rand_at	[REDACTED]
consent_to_gs_at	blank
second_randomized_at	[REDACTED]
withdrawn_at	blank
ineligible_at	blank
no_show_at	blank
refused_at	blank

Scheduled Reminders
No Reminders scheduled

Survey Codes

7V59P2
Pre-Visit 1 Parent Questionnaire ver2

SECAJ8
Post-Visit 1 Parent Questionnaire ver 3

B62SSF
Baseline Intake v2

Apart from “Force Set...,” all these statuses are final and *cannot be changed*. “Force Set...” returns participants to initial “Referred” status and resets all data.

A participant’s status can be changed manually by clicking the “Change Status.” This will open a drop-down menu.

Change Status ▾ More ▾

- Force Set Participant to Referred
- Mark Refused
- Mark Withdrawn
- Mark Withdrawn by Investigator
- Mark Ineligible
- Mark No Show
- Mark Failed Approach
- Mark No Approach

For whichever option is selected, a dialog box will appear. Select the appropriate sub-type of status change and type in a reason. Click “Save Changes” to complete the status change.

Add Refusal Type

Type: At enrollment call (Intervention 1)

Reason: [REDACTED]

Save changes

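### As written, refusing a single survey is enough to give a randomized family the final status Refused; such a refusal should be recorded against the task, not the participant

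*Protocol*

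**What the plan says.** Under Mark Participant as Refused Manually, a participant's "status should be manually marked refused when a participant refuses to complete a study activity". The section adds: "This is initiated by the participant and occurs during a data collection activity (e.g., enrollment call, pre-visit survey, post-visit survey". It gives no minimum number or type of activities and no alternative at task level.

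Three places govern what the status means:

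- The footnote to that section makes manually entered statuses final and adds: "Only tracking system administrators can change these statuses once they are set".
- Status Dates, in Using the Tracking System, says that "all these statuses are final and" not open to change. The one exception is the Force Set option, which returns the participant to Referred and resets all data.
- Key Terminology: Task v. Status allows one status at a time and says that "final statuses do not change and indicate a" participant's end position in relation to the study.

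The Withdrawal section covers a participant who asks to leave: "This request is initiated by the participant and occurs at any time". Appendix III states that the analysis will be by intention to treat.

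**The concern.** Both in-clinic surveys fall after Randomization 1 and before Randomization 2. A parent who declines the tablet survey may be declining only that form. The rule nevertheless moves the whole participant to an end state, so partial non-response can become complete loss of a randomized family. Later outcomes that the family never declined to give are then not collected, and the family may not be offered Randomization 2.

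An intention-to-treat analysis keeps each family in its assigned arm but cannot restore outcomes that were never sought. The rule also separates Refused from Withdrawn mainly by the moment at which the event occurs, and not by what the parent wants. A parent who asks to leave while being handed a survey fits both definitions.

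**Working it through.** The protocol gives no figure that depends on this rule, so the check is a comparison of its sections.

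**Step 1: what triggers the status.** The trigger is an active refusal by the participant during data collection. One refused activity is enough on the wording. A form that is forgotten, late or unreturned is not covered. The Post-RoR 2 Week and 6 Month Parent Survey sections have late forms entered all the same.

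**Step 2: whether the status ends participation.**
- Only one status is held at a time, so Refused replaces Parent Consented.
- A final status is described as the participant's end state. For two other final outcomes (not selected, and ineligible child or parent) the protocol says that nothing more need be done.
- Where the consequence of Refused is spelled out (If the Parent Declines, in person and by phone), consent form 1 or the HIPAA form has been declined and the family leaves the study. Footnotes there send staff back to the general instruction on marking participants refused.
- No milder form of Refused is defined for a declined survey, but its consequence is not written down either. Appendix II holds the status flowchart as a figure that was not available for this check, and it may show more.

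Loss of later steps is therefore the natural literal reading, but it remains an inference.

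**Step 3: what a literal reading forfeits.** The consent script asks for five parent surveys: intake, pre-visit, post-visit, 2-week and 6-month.
- Refusal at the pre-visit survey: 5 − 2 = 3 later surveys, plus Randomization 2.
- Refusal at the post-visit survey: 5 − 3 = 2 later surveys, plus Randomization 2.
- Refusal at the 2-week survey (the example list is open-ended): 5 − 4 = 1 later survey.

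The 2-week and 6-month surveys go only to families who consent to Randomization 2, so these are maxima.

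**Step 4: how other refusals are handled.**

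| Declined | Section | Result |
|---|---|---|
| Pre- or post-visit survey | Mark Participant as Refused Manually | Participant set to Refused |
| Single survey questions | Opening instructions of both surveys | May be skipped |
| Audio recording | Parent Permission to Audio Tape Clinic Visit | Task saved unsigned; visit goes on |
| Blood draw | Saliva Collection for Child Participants | Saliva kit offered |
| Saliva sample | Appendix VIII | No sequencing; surveys can continue |
| Sequencing consent or assent (form 2) | If the Parent Declines; Obtaining assent | Follow-up surveys continue |
| Consent form 1 or HIPAA | If the Parent Declines | Refused; participation ends |

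The first row is out of line with the next five. A parent who accepts the tablet and skips questions stays in. A parent who declines the tablet is marked Refused.

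**Step 5: whether the status can be undone.** The footnote says administrators can change it. Status Dates says it cannot be changed, short of a reset that wipes the record. These two statements disagree.

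**The case against.** Parents are screened for willingness to complete all surveys and consent to five of them, so treating an explicit refusal as Refused has an operational logic. Many difficult visits are problems of time, and the protocol has other routes for those, including phone consent where the child needs no assent. The status-change screen asks for a sub-type and a reason, and a request to withdraw needs its own form, so Refused and Withdrawn are partly distinguishable already.

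The last point stands: the two statuses are not indistinguishable. But the reason is stored at participant level, and nothing requires it to separate declining this form from declining the study. The screening argument does not explain why declining other consented elements leaves the family in.

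A reader might go further in five ways that the documents do not support:

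- **That the status is irreversible.** The footnote lets administrators change it.
- **That one missed questionnaire is enough.** The trigger is an active refusal.
- **That the intake survey is treated more leniently.** For intake the protocol says: "If the participant cannot complete the survey in clinic, parent should be provided with another Intake Survey with a labeled envelope with prepaid postage". That concerns non-completion. Outright refusal of intake is not exempted, because the example list is open-ended.
- **That Appendix III expects unequal loss.** It records a concern that some prep-arm participants from certain demographic groups may drop out before Randomization 2. It does not predict this and does not discuss survey refusal.
- **That the loss can be sized.** Assumed refusal rates of 2% and 5% of the planned 850 would give 0.02 × 850 = 17 and 0.05 × 850 = 42.5, about 43 families. Nothing in the protocol supports those rates, and not every enrolled family reaches an in-clinic survey.

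**Conclusion.** The point holds in a limited form. The instruction does not separate refusing one activity from refusing further participation. Read literally, it allows one declined survey to close out a family already in Randomization 1, with a loss of up to three later parent surveys and possibly Randomization 2. It fits poorly with the stated intention-to-treat analysis and with the protocol's own handling of declined recording, blood, saliva and sequencing.

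The conclusion rests on taking final status to mean that participation stops, which the protocol states only for declined consent form 1 or HIPAA. The number of families affected is unknown. The change should be made because the loss is avoidable and cheap to prevent; a large loss has not been shown.

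**What to change.** 1. In Mark Participant as Refused Manually, limit Refused to a parent or child who declines the study, or a consent, HIPAA or assent step that ends participation.
2. Record refusal of a single survey against that task, with a reason. The reminder-call task already has a Not Done outcome that could serve as the model. Leave the participant status unchanged and continue with the next scheduled step.
3. In Withdrawal, use Withdrawn whenever the parent asks to leave the study, including during a data collection activity.
4. Reconcile the footnote on administrators with the statement in Status Dates, and check that the Appendix II flowchart agrees with the revised rule.

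The cost is a few sentences in three sections and a task-level reason code in the tracking system. The downside is continued contact, on the existing schedule, with a few families who declined one form; they remain free to withdraw at any time.
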